##### Main analysis

Start time for time until new contralateral breast cancer: 2 year after randomization

##### Sensitivity analyses

Start time for time until new contralateral breast cancer: randomization

#### 3.6.3. Time to secondary carcinoma

This is defined as the time from randomization or from two years after randomization to first occurrence of new secondary cancer without new breast cancer (local or contralateral). Subjects without secondary cancer event would be censored at last date when they were known to be secondary cancer free.

##### Main analysis

Start time for time until new second cancer: 2 year after randomization

##### Sensitivity analyses

Start time for time until new second cancer: randomization

### 3.6.4. Time to first clinical fracture

This is defined as the time from two years after randomization to first clinical fracture. Patients without clinical fractures were censored at their last therapy visit (maximum approximately 5 years after randomization).

## 3.7. Safety evaluation

Analyses of the safety data are based on the SAF population. Only serious adverse events (SAEs) and adverse events (AEs) leading to discontinuation of the therapy are collected in this trial. Frequencies of serious adverse events will be summarized descriptively per treatment arm and in total. Patient listings of SAEs and of AEs leading to discontinuation of the therapy will be given. Change in tumor markers CEA and CA 15-3 will be descriptively summarized (e.g., means, median, standard deviations, ranges).

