7.2. Examination parameters during the study

7.2.1. After 6 months (Arm A and B)

1. Clinical examination
2. Survey of fracture rate
3. Adverse events leading to discontinuation of therapy
4. Severe adverse events

The time frame for these examinations is defined as +/- 6 weeks.

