9.1 Definition of “adverse event – (AE)”

An adverse event is the occurrence of a disorder or exacerbation of a pre-existing condition in the context of a clinical study and is independent of a possible causal relationship with the administration of the trial drug. Disorders may be subjective and objective symptoms of the disease, including laboratory abnormalities. Adverse events leading to discontinuation of therapy must be documented in both the medical history and in the CRF.

With the exception of AEs that lead to discontinuation of therapy and fractures, all other AEs that are non-serious are not documented in the CRF within this study. However, it is mandatory to record all adverse effects in the patient’s medical file.

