10.5. Safety analysis

The safety analysis is based on all randomised patients who started the therapy. All serious adverse events, adverse events leading to therapy discontinuation and fracture rates observed during or after therapeutic administration of the study drug are recorded. The worst value per patient is included in the analysis.

[figure not shown]
The laboratory data measured is described and maximum and minimum measurements are presented over time or by maximum deviations from the normal range. In addition, absolute and percentage changes from the baseline measurement values and maximum fluctuations over time are described.

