7.3. Follow-up

After the therapy is complete, follow-up examinations are carried out at 36, 48 and 60 months in Arm A analogously to the therapy examinations in the Arm B. After the 60th monthly visits, the standardised follow-up examinations are carried out at yearly intervals (+/- 6 months) over a period of 5 years for both arms.

1. Physical examination
2. Bilateral mammogram (unilateral mammogram in the case of mastectomy)
3. Serious adverse events (see 9.1 and 9.2.4)

Affected protocol point:

- 1.2. Flow chart (page 12)

Old text:

1. Separate specification for patient history and clinical examination
2. No detailed information for gynaecological examination

Amended text:

1. Change to physical examination
2. Gynaecological examination with asterisk * in screening: * Including ultrasound (exception: status post hysterectomy) or ** at the therapy visits: ** "Follow-up examination in accordance with the current state of scientific knowledge"

Justification for the amendment:

- Points 9a–9f in the inclusion criteria are handled in a separate point (i.e. Amendment in point 1 "Patient selection" or additional point 5.4 "Diagnosis") (reason: The above-mentioned examinations from point 9 are not actual inclusion criteria but rather constitute guidelines for how inclusion criteria 3 and 4 are should be ensured.)
- Change of description in the exclusion criteria: "Manifest secondary malignancy or status post secondary malignancy between the time of initial diagnosis and randomisation" to "manifest secondary malignancy or status post secondary malignancy" (reason: misleading description; there are patients who were included status post secondary cancer who had to be set to ineligible.)
- The gynaecological examination at screening has been supplemented by a mandatory ultrasound examination (reason: accurate clarification of any pathological changes which otherwise could be attributed to the study medication is possible at inclusion.)
- The time frame for the gynaecological examination is extended to 6 months (reason: it is not feasible to obtain findings in a time frame of one month prior to randomisation.)

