### 3.3.3. Safety (SAF) population

Safety analyses will be based on the SAF population and include all enrolled and treated patients. Hence, all patients who were randomized and received at least one dose of study treatment.

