### 3.6. Secondary endpoint evaluation

All secondary endpoint analyses will be based on the ITT population. For all secondary endpoints, 2-sided log-rank tests (unstratified) will be used to test for differences between 2 additional years anastrozole versus 5 additional years anastrozole at an overall alpha level of 0.05. No multiplicity adjustment will be applied for the secondary endpoints.

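### SAP 3.7 wrongly says that only SAEs and discontinuation AEs are collected, and it omits, undeclared, the protocol's safety summary of fractures in treated women

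*SAP*

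**What the plan says.** SAP 3.7, on safety data: "Only serious adverse events (SAEs) and adverse events (AEs) leading to discontinuation of the therapy are collected in this trial". The section then plans SAE frequencies by arm, listings of SAEs and of AEs that stopped therapy, and summaries of two tumour markers. Its analysis set is defined in SAP 3.3.3: "Safety analyses will be based on the SAF population and include all enrolled and treated patients".

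The protocol says otherwise in three places.

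- Section 9.1, on what the CRF covers: "With the exception of AEs that lead to discontinuation of therapy and fractures, all other AEs that are non-serious are not documented in the CRF".
- Section 10.5, on content: "All serious adverse events, adverse events leading to therapy discontinuation and fracture rates observed during or after therapeutic administration of the study drug are recorded". On the analysis set: "The safety analysis is based on all randomised patients who started the therapy". It then takes one worst value per patient into the analysis.
- Section 7.2.1 lists a "Survey of fracture rate" at month 6. Section 7.2.2 as amended by Amendment 1 repeats it at months 12, 24, 36, 48 and 60. Section 7.3 as amended adds that "follow-up examinations are carried out at 36, 48 and 60 months in Arm A analogously to the therapy examinations in the Arm B".

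Elsewhere the SAP treats fractures as collected data. Section 3.1.2.2 has an imputation rule for partial fracture dates. Section 3.6.4 defines time to first clinical fracture from two years after randomisation, censored at the last therapy visit (about year 5). For its population, section 3.6 says: "All secondary endpoint analyses will be based on the ITT population".

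**The concern.** Protocol 2.3.2 names fractures as significantly more common with anastrozole than with tamoxifen (5.8% against 3.7% overall in its Table 2). This trial compares longer with shorter anastrozole. Fracture rates are also one of only three clinical items in the protocol's safety analysis.

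The SAP's safety section omits them from its account of what is collected and plans no output for them. SAP section 4, which is where departures from the protocol are listed, covers only the interim and advanced analyses. No amendment removes fractures from protocol 10.5.

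What is at stake is the safety description. A report written to SAP 3.7 would show SAE tables and listings, which leave out non-serious fractures that did not stop therapy.

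**Working it through.** **Step 1. Is the sentence true?** Protocol 9.1 names two exceptions to the rule that non-serious AEs stay out of the CRF: AEs that stop therapy, and fractures. SAP 3.7 keeps the first and drops the second. The survey at month 6 and then at months 12 to 60 is still in force, in both arms. SAP 3.1.2.2 and 3.6.4 depend on those data. Read literally, the sentence is false.

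**Step 2. Where are fractures analysed?**

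| SAP section | Population | Clock starts | Used in |
|---|---|---|---|
| 3.6.4, with 3.6 | ITT (but see below) | year 2 | advanced and final |
| 3.8.2, multivariable | ITT | not stated separately | exploratory |
| 4.2.2.2 | ITT (4.2.1) | randomisation | advanced only |
| 4.2.3.1 | adherent part of ITT | randomisation | advanced only |
| 3.7 | SAF | no fracture output | none |

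No row gives a fracture summary in all women who started drug. SAP 4.2.2.2 does not name fractures, but it stands under a heading that covers primary and secondary endpoints, so I read it as including them.

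The first row is not secure for the final analysis. SAP 4.2.1 assigns that analysis to the protocol's set: eligible women with a follow-up examination who were recurrence-free at two years. SAP 3.6 says ITT. The two conflict. The protocol's planning figure for relapse in the first two years is 5%, that is 3,500 × 0.05 = 175 women, who would be left out if 4.2.1 governs.

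**Step 3. How much on-drug time lies inside the 3.6.4 window (months 24-60)?** Inputs: 2 and 5 years of treatment (protocol section 4) and 3,500 women (10.1). Assumed: 1,750 per arm, scheduled time, no losses.

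- Arm A: 0 of 24 months. Arm B: 36 of 60 months.
- On-drug patient-years: 1,750 × 2 + 1,750 × 5 = 12,250.
- Inside the window: 1,750 × 3 = 5,250 (43%). Outside: 7,000 (57%).
- Surveys before or at the start of the window: months 6, 12 and 24, three of six.

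An illustrative count for years 0-2 uses the 5.8% in protocol Table 2 over a mean of 30 to 36 months, with a constant rate assumed.

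- Rate: −ln(1 − 0.058)/2.5 = 2.39, or /3.0 = 1.99, per 100 patient-years.
- No losses: 3,500 × (1 − exp(−2 × rate)) = 163 or 137 women.
- With the 7% drop-out of protocol 10.1 read as yearly (no time unit is given), d = −ln(0.93) = 0.0726: 3,500 × rate/(rate + d) × (1 − exp(−2(rate + d))) = 152 or 127.
- Range: 127 to 163 women, or 64 to 82 per arm. This includes serious fractures, which would also appear in SAE tables.

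These figures describe what the year-2 starting point leaves out. They do not measure the difference between ITT and SAF.

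**Step 4. Does the advanced analysis have the full survey?** The maximum treatment phase ends in June 2015 (Amendment 3) or December 2015 (SAP 2.1.1.1). Adding the 6-month visit window gives December 2015 or June 2016. The cutoff is 30 June 2016 (SAP 3.2.2). On the scheduled dates, all month-60 surveys are in.

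**Step 5. Could SAE tables stand in for the survey?** No. Under protocol 9.3.2, once drug has stopped an SAE is reported only within 30 days, or later if a link with anastrozole cannot be ruled out. In years 2-5 that limit applies to Arm A, while Arm B is still on drug with full reporting. Protocol 9.5 also exempts accidents that are solely a third party's fault.

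**The case against.** The strongest reply is that this is loose wording with little effect. The sentence concerns adverse events, and the same paragraph goes on to tumour markers, so it cannot mean all safety data. The fracture endpoint stands in the section just before it. The protocol also treats fractures largely as an efficacy variable: they are among the efficacy parameters in 1.1, are defined in 8.1, and are tested by log-rank in 10.4. SAP 3.6.4 keeps that test. The ITT set contains every treated woman who gave consent, serious fractures reach the SAE tables, and protocol 10.5 prescribes no particular fracture table.

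Much of this stands. A reader might infer from SAP 3.7 that fracture data were not collected or will be lost, or that the fracture test is biased. The documents support neither: the data are in the CRF and the arms are compared in 3.6.4. A reader might also infer that fractures before year 2 are never analysed. The advanced analysis covers them through 4.2.2.2. It would likewise be wrong to take the 57%, or the 127 to 163 women, as the size of the safety gap, because both follow from the year-2 clock in 3.6.4.

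What does not stand is the suggestion that nothing is missing. Protocol 10.5 is headed as the safety analysis, lists fracture rates beside the other two clinical items, and brings a per-patient value into the analysis, so it goes beyond data collection. An ITT result that mixes in women never dosed is not that summary, and SAP section 4 does not say that it was replaced.

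**Conclusion.** The point holds as a minor one. The SAP 3.7 sentence is wrong, and a safety item that the protocol specifies for treated patients was dropped without being declared.

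The loss is descriptive and has two parts. There is no fracture summary in all treated women. In the final analysis there is also no planned fracture analysis of years 0-2, which are all of Arm A's scheduled time on drug; only fractures reported as SAEs or as AEs that stopped therapy would appear. The population conflict between SAP 3.6 and 4.2.1 may narrow the final fracture results further.

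The between-arm fracture comparison is not affected. The SAF-specific gap cannot be sized, since the documents give neither the number of women never dosed nor the non-serious share of fractures. The conclusion rests on the text alone. The coverage figures additionally assume equal arms, scheduled durations and no losses.

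**What to change.** 1. Change the SAP 3.7 sentence to: *SAEs, AEs leading to discontinuation of therapy, and fractures are collected.*
2. Add to SAP 3.7 one descriptive table on the SAF population, by arm: women with at least one fracture from first dose to month 60. Build it from the fracture survey and not from SAE reports, for the reason in step 5.

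A split at month 24, rates per 100 patient-years, and a split by the four sites in protocol 8.1 are optional. Site counts may be too small to test. Declaring the omission in section 4 would not be enough alone, because the sentence would stay false and the summary of a known harm would still be missing.

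The cost is one sentence and one table from data already in the CRF, with some overlap with the ITT fracture results. It needs no new data, test or alpha.

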5.4. Premature termination of the clinical study

5.4.1. Premature termination in an individual case

Reasons leading to study discontinuation are:

1. Withdrawal of patient consent
2. Occurrence of intolerable adverse events
3. Occurrence of relapse, secondary cancer or death of the patient
4. Lack of compliance or cooperation of the patient
5. Serious protocol violation
6. Other personal reasons for the patient (e.g. change of location); there is usually the possibility of ongoing care at another ABCSG study site
7. Patient no longer attends (lost to follow-up): the maximum time frame for this is
 - In the therapy phase: +6 months calculated from the scheduled visit date (see 6.5.)
 - In the follow-up phase: +12 months from the scheduled visit date

The investigator must make every effort to establish contact with the patient.

Each patient has the right to withdraw their consent to take further part in the clinical trial at any time and without giving reasons. You will not be disadvantaged as a result. The investigator will attempt to ascertain the reasons for the discontinuation, but the patient's rights must not be violated. The time of the discontinuation, the results to date, and, if known, the reason for the patient's discontinuation should be documented in the patient file and the CRF. If a patient wishes to withdraw from the study, they must be asked whether or not they agree to the further use of their clinical data (in particular to disease-related events and follow-up) for study-related purposes.

The investigator may also terminate the trial if he no longer deems the patient's participation to be justified e.g. from a medical point of view. The date and reason for discontinuation, as well as all observations gathered up to the point of discontinuation are to be recorded in the medical history and CRF.

The investigator will continue to observe patients who were removed from the study due to intolerable adverse events until these have resolved or findings have normalised.

All patients, regardless of whether the treatment was discontinued prematurely or not, will receive follow-up care as per the study protocol. Data will be collected and documented in accordance with the FUP guidelines (see 7.3.).

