9.3.2. Reporting during follow-up or after discontinuation of therapy

The occurrence of serious adverse events in patients, in whom the study drug / study participation has been discontinued or terminated or the therapy has ended in line with the protocol only need to be reported if the adverse event occurred

- Within 30 days of discontinuing the study drug (drug incidents that are a causally linked to a follow-on therapy are not reported)
- More than 30 days after discontinuing the study drug, but the investigator cannot rule out a causal link with the previous therapy (anastrozole).

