7.2.2. After 12, 24, 36, 48 and 60 months

1. Physical examination
2. Survey of fracture rate
3. Adverse events leading to discontinuation of therapy
4. Serious adverse events
5. Development of hepatic, renal insufficiency
6. Optional TU marker: CEA, CA 15-3
7. Gynaecological examination
8. Radiological examinations
 - Sonography of the abdomen or abdominal CT
 - Chest x-ray or CT
 - Bilateral mammogram (unilateral mammogram in the case of mastectomy)
9. Bone density measurement (optional)

Affected protocol point:

- 7. Implementation
- 7.3. Follow-up (page 28)

Old text:

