##### 4.2.3.1. *Adherence to prescribed therapy*

Adherence is defined as the consistency of taking protocol treatment. Treatment duration will be calculated on the basis of documented start and end of therapy. Early/Late end of therapy is defined as departure from prescribed duration of arm therapy for more than or less than 6 months.

Patient is adherent if duration of therapy is not shorter than 6 month and not longer than 6 month then prescribed therapy for therapy group or has an early end of therapy with reason recurrence or death.

Patient with an early/late end of therapy with reason for end of therapy different from recurrence/death are defined as non-adherent. Patients who died during treatment period and do not have reported treatment discontinuation before their death are considered adherent. Patients who never started therapy treatment are consider non-adherent.

The adherent population consists of all patients from the ITT population who are adherent to prescribed treatment. Analyses for the primary and for all secondary endpoints will be repeated based on the adherent population with time at randomization as start point.

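### By-arm SAE frequencies have no stated collection window, and the adherence rule does not say whether a second cancer is a recurrence; either gap can create an arm difference with an inert drug

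*SAP*

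**What the plan says.** **SAE tables.** SAP 3.7 works on all randomised patients who took at least one dose (SAP 3.3.3) and plans that "Frequencies of serious adverse events will be summarized descriptively per treatment arm and in total". It names no period. The protocol passages that might supply one differ:

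- Protocol 9.3.2 requires a report after the end of therapy if the event falls "Within 30 days of discontinuing the study drug", or later only if the investigator cannot exclude a link to anastrozole.
- Protocol 5.4.1: "All patients, regardless of whether the treatment was discontinued prematurely or not, will receive follow-up care as per the study protocol".
- Protocol 10.5 counts SAEs "observed during or after therapeutic administration of the study drug".
- Amendment 1, section 7.2.2, lists SAEs at visits headed "After 12, 24, 36, 48 and 60 months", with no restriction by arm.
- Amendment 1, section 7.3: "follow-up examinations are carried out at 36, 48 and 60 months in Arm A analogously to the therapy examinations in the Arm B". Its follow-up list then has "Serious adverse events (see 9.1 and 9.2.4"), but the protocol has no section 9.2.4.

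**Adherent population.** SAP 4.2.3.1 compares each patient's treatment time with her own arm's duration, with a 6-month tolerance. An early stop is excused only for recurrence or death: "Patient with an early/late end of therapy with reason for end of therapy different from recurrence/death are defined as non-adherent". DFS and all secondary endpoints are then re-analysed in the adherent patients, with time counted from randomisation.

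**The concern.** Planned therapy lasts 2 years in one arm and 5 in the other. A count that follows time on drug therefore gives Arm B a window about two and a half times as long. Deaths not due to the underlying disease and new malignancies are among the SAEs (Protocol 9.2, 9.5), so events accrue in both arms whatever the drug does. A by-arm SAE table will be read as the safety cost of 5 against 2 years. If 9.3.2 governed what was collected, harm could not be told apart from window length.

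The adherence rule raises a similar problem. Amendment 1, section 5.5.1, lists secondary cancer beside relapse and death as a reason to discontinue, so it is a distinct stop reason. SAP 3.5.1, however, uses disease recurrence as shorthand for all non-fatal DFS events, second cancer included. Both readings are open. Under the narrow one, a patient who stops because of a second cancer is removed together with her endpoint event. That can happen up to year 1.5 in Arm A but up to year 4.5 in Arm B. The rule does not name contralateral breast cancer either.

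**Working it through.** The plan gives no figure for either ratio, so there is none to reproduce. All calculations assume no drug effect. Event and stopping rates are assumptions, because the documents do not give them.

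**(a) SAE window under Protocol 9.3.2**

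Inputs: T = 2 or 5 years of therapy (SAP 2.1.1); w = 30 days = 0.082 years (Protocol 9.3.2); SAE rate λ = 3–12% a year and exponential stopping d = 0–10% a year (assumed).

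Window = min(T, stopping time) + w, so

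P(at least one SAE) = 1 − e^(−λw) × [d/(λ+d) + λ/(λ+d) × e^(−(λ+d)T)].

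- λ = 3%, d = 0: Arm A 1 − e^(−0.03 × 2.082) = 0.06055; Arm B 1 − e^(−0.03 × 5.082) = 0.14141; ratio 2.34.
- λ = 12%, d = 10%: Arm A 0.2021; Arm B 0.3701; ratio 1.83.
- Mean window over the grid: 1.89–2.08 years in Arm A, 4.02–5.08 in Arm B.

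Now let a fraction f of the SAEs after the window, up to month 60 plus 30 days, also be reported. The effective window becomes W + f × (5.082 − W). For λ = 3%, d = 0, f = 0.25, Arm A has 2.082 + 0.25 × 3 = 2.832 years, P = 0.08145, and the ratio is 0.14141/0.08145 = 1.74.

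| Fraction f of later SAEs reported | B/A ratio over the grid |
|---|---|
| 0 | 1.83–2.34 |
| 0.10 | 1.64–2.05 |
| 0.25 | 1.44–1.74 |
| 0.50 | 1.22–1.39 |
| 0.75 | 1.09–1.16 |
| 1.0 (same collection in both arms) | 1.00 |

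**(b) Adherent population**

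Inputs: entry December 2003 to June 2010, taken as uniform over 6.5 years; cut-off June 2016 (SAP 3.2.2), 12.5 years after the start; cap 10.5 years (SAP 3.5.2). Follow-up = min(12.5 − U(0, 6.5), 10.5): minimum 6.0, mean 8.9, median 9.25 years.

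Rough check for the narrow reading: with a constant second-cancer hazard, Arm A loses the events of the first 1.5 years and Arm B those of the first 4.5. With follow-up F the ratio is about (F − 4.5)/(F − 1.5). At F = 8.9 this is 4.4/7.4 = 0.59; at F = 10 it is 5.5/8.5 = 0.65.

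Simulation, 1 million patients per arm and setting: recurrence 1.8%, death 0.6%, second cancer 0.4, 0.8 or 1.2%, unrelated stops 0, 3, 6 or 10%, all per year.

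| Reading of recurrence | Second-cancer B/A | DFS B/A |
|---|---|---|
| Excludes second cancer; 100% of second cancers end therapy | 0.61–0.63 | 0.88–1.06 |
| Same; 75% end therapy | 0.72–0.74 | 0.91–1.08 |
| Same; 50% end therapy | 0.82–0.83 | 0.95–1.09 |
| Includes second cancer | 0.99–1.12 | 1.00–1.12 |
| Includes second cancer, 2-year landmark | 0.98–1.02 | 0.99–1.01 |

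In the first row the rule excludes 0.6–15% of Arm A and 1.7–38% of Arm B. The ratio in the fourth row can exceed 1 because a patient without an event must stay on drug to year 4.5 to remain in Arm B's set, but only to year 1.5 in Arm A. A patient whose event comes before any unrelated stop remains in either arm. Arm B therefore keeps relatively more events. The landmark removes this and leaves out 5.4–19.9% of each arm.

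**The case against.** On (a), Protocol 9.3.2 governs what an investigator must report to the sponsor, which need not be what was collected at visits. Amendment 1 is the later text, and it sets the same visits to month 60 in both arms with SAEs on the list. SAP 3.6.4 censors fractures at the last therapy visit, at most about 5 years in either arm, which fits a common schedule. Equal collection is therefore at least as well supported, and it gives a ratio of 1.0. This stands as a reason not to claim a bias. It does not supply the missing rule: the SAE row of the flow chart in Protocol 1.2 refers back to section 9, and amended 7.3 refers to a section that does not exist.

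On (b), 0.6 is the extreme case, needing the narrow reading and every second cancer ending therapy. Within the SAP the wide reading is the more natural one, and the form's categories for end of therapy, which the documents do not show, might settle it. This too stands, but the rule as written does not decide the matter, and the wide reading has its own null bias.

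On reach, the SAE table carries no test and the adherent analysis is exploratory. That is correct and limits the weight of both points. The landmark version is close to the planned analysis from year 2 and says nothing about adherence to 5 years. That is why it should be added beside the planned adherent analysis and not replace it.

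**Conclusion.** Both gaps are real and should be closed. For SAEs the defect is an unreconciled window, not a demonstrated bias. The null B/A ratio is 1.0 if collection was equal and 1.8–2.3 if 9.3.2 governed and nothing later was reported; partial late reporting falls between. This rests on constant, equal SAE rates of 3–12% a year and stopping of 0–10% a year.

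For the adherent population, the narrow reading gives a null second-cancer ratio of about 0.6 in favour of Arm B if every second cancer ends therapy, and 0.82–0.83 if half do. The DFS range under that reading, 0.88–1.09, spans 1, so no direction is shown for DFS. Under the wide reading the ratios can reach about 1.12 against Arm B.

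The primary DFS test and the ITT second-cancer analysis, which has its own definition and censoring (SAP 3.6.3), are not affected.

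**What to change.** **SAP 3.7.** Reconcile Protocol 5.4.1, 9.3.2 and 10.5 with amended 7.2.2 and 7.3, and state the SAE collection rule that applied in each arm. Beside the frequencies, report SAEs per 100 patient-years of actual reporting window. Show months 0–24 separately as the like-for-like comparison, and label later data descriptive wherever collection differed.

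**SAP 4.2.3.1.** Define recurrence to cover every DFS event, second and contralateral cancers included, so that no patient is removed for having an endpoint event. Keep the full-duration adherent analysis, but say that it is subject to selection and is not evidence of a treatment difference. Add a 2-year landmark version: patients event-free at year 2, with adherence judged up to year 2.

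**Cost.** SAP wording and some table programming; no new data. If collection differed, no like-for-like SAE comparison exists after month 24. The landmark set leaves out about 5–20% of each arm, equally at the assumed rates, and does not measure adherence to the full 5 years.
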